6.2.10 CGII-C and CGII-P

Clinical Global Impression of Improvement –Clinician (CGII-C), or Clinical Global Impression of Improvement –Patient/Caregiver (CGII-P): A 7-point Likert scale completed by the Clinician

or Patient/Caregiver representing the degree to which the subject's epilepsy symptoms have changed relative to baseline. On the CGII-C, 1=very much improved and 7=very much worse.

Frequency and percentage of the responses will be summarized by visit for CGII-C and CGII-P separately. The analysis will be conducted by cohort separately. A subject data listing will be provided.

6.3 ANALYSIS OF MONTHS 1 – 3

In order to explore early signals of efficacy, the seizure and cluster analyses described above will be repeated using just the first 3 months of the post-baseline period, defined as the first 90 days following the first day of treatment (Study Days 2 to 91).

7. SAFETY ANALYSIS

All safety analyses will be performed by cohort and overall in the Safety Population. The highest percentage of the maximum allowable daily dose that subjects received will be summarized with descriptive statistics. The cumulative dosage that subjects received will be summarized with descriptive statistics, separately for subjects receiving their dosage on a mg/kg basis and those receiving it on a mg basis. For subjects who received dosing on a mg/kg basis at the start of the study and then switched to a mg basis, the doses with a mg basis will be converted to a mg/kg basis by dividing the mg by the subjects' most recent weight prior to the mg basis. A subject data listing will be provided with full details of the study drug dispensation.

Safety assessments include:

- AEs
- Clinical laboratory tests
- Vital signs including temperature, blood pressure, pulse rate, and weight
- Neurological and physical examinations
- 12-lead ECG
- EEG
- C-SSRS

Baseline is defined as the last non-missing value obtained before the first treatment. Assessments performed at multiple post-baseline time points will be summarized at each time point for which they are scheduled. The listings will include any assessments performed at unscheduled time points.

7.1 ADVERSE EVENTS

Adverse events will be coded by SOC and Preferred Term using MedDRA®, version 16.0. The verbatim term will be included in the AE listings.

A treatment-emergent adverse event (TEAE) is defined as an AE that starts or worsens on or after the first dosing day of study drug. The AE analyses for the main 26-week open-label treatment period of the study will include AEs that start during that period and will not include AEs that start during the OLE period of the study; i.e. they will not include any AEs starting on or after the first dosing day of the OLE period. Pre-treatment emergent AEs will be summarized

by SOC and Preferred Term. Only TEAEs will be included in the other summary tables. Pre-treatment AEs and TEAEs will be presented in subject data listings.

The TEAEs will be summarized as the number of events and the number (percentage) of subjects with TEAEs. Subjects who report the same Preferred Term on multiple occasions will be counted once for the Preferred Term: under the highest severity (severe > moderate > mild) when summarized by severity and under the closest relationship (related > probably related > possible related > unlikely related > not related) to study drug when summarized by relationship.

Treatment related AEs are defined as those events recorded in the CRF as 'Related', 'Probably Related' or 'Possibly Related'; AEs recorded in the CRF as 'Unlikely Related' or 'Not Related' will be considered as not related to treatment. TEAEs with missing relationships will be considered as related.

If a subject reports multiple Preferred Terms for an SOC, the subject will be counted only once for that SOC. For the counting of events, all the Preferred Terms will be included in the counts, even when subjects have multiple Preferred Terms.

TEAEs will be summarized as below.

- An overview table, including number of events and subjects with
 - TEAEs
 - serious AEs (SAEs)
 - Treatment related TEAEs
 - TEAEs by severity
 - TEAEs leading to study discontinuation
 - TEAEs leading to death
- TEAEs by SOC and Preferred Term
- TEAEs by SOC, Preferred Term, and Severity
- Study drug related TEAEs by SOC, Preferred Term
- SAEs by SOC and Preferred Term
- TEAEs leading to study drug discontinuation by SOC and Preferred Term
- TEAEs by Preferred Term

All AE tables will be sorted by SOC and Preferred Term in decreasing frequency of the number of subjects in the combined cohorts. In cases of ties the sorting will be alphabetical.

For purposes of determining treatment emergent events, missing start dates will be imputed as shown in the following table; however, the actual dates, not the imputed ones, will display in the data listing.

Partial Missing Start or Stop Date	Imputed Start Date	Imputed Stop Date
Missing year, month, and day	First dose date	
Missing month and day, and the year is present	First dose date if the year is the same as the year of first dose date, else first dose date of the OLE if the year is the same as the year of the first OLE dose date, else January 1 of the AE start year.	December 31 of that year
Missing day, but year and month are present	First dose date if the year and month are the same as the year and month of first dose date, else first dose date of the OLE if the year and month are the same as the year and month of the first OLE dose date, else the 1 st of the AE start month.	Last day of that month
Missing month, but year and day are present	Assume day is also missing and impute as above	Missing month imputed as December

If an imputed start date is later than the stop date, then the stop date (after any needed imputations) will be used instead for the imputed start date.

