10.5.2 Evaluating and Recording of Adverse Events

At each visit all adverse events that are observed, elicited by the Investigator, or reported by the subject, will be recorded in the appropriate section of the CRF and evaluated by the Investigator.

Minimum information required for each AE includes type of event, duration (start and end dates), severity, seriousness, causality to study drug, action taken, and outcome.

Severity of AEs will be graded by the Investigator using the following criteria as guidelines:

1. Mild: Nuisance, barely noticeable.

2. Moderate: Uncomfortable, troublesome symptoms not significantly

interfering with daily activities or sleep.

3. Severe: Symptoms significantly interfere with daily activities or sleep.

The relationship of the AE to the study drug should be specified by the Investigator, using the following definitions:

1. Not Related: Concomitant illness, accident or event with no reasonable

association with study drug.

2. Unlikely Related: The event has little or no temporal sequence from administration

of the study drug, and/or a more likely alternative etiology exists.

3. Possibly Related: The event follows a reasonable temporal sequence from

administration of study drug but which could also be explained

by concurrent disease or other factors or medications

4. Probably Related: The event follows a reasonable temporal sequence from

administration of study drug, unlikely to be attributed

to concurrent disease or other factors or medications. A clinically

reasonable response may be observed if the study drug is

withdrawn or dose reduced.

5. Definitely Related: the event follows a reasonable temporal sequence from

administration of study drug and is definitive

pharmacologically; cannot to be attributed to concurrent disease or other factors or medications. A clinically reasonable response should be observed if the study drug is withdrawn or dose reduced.

When applicable, a syndrome ("flu syndrome") that describes a constellation of AEs should be recorded in the CRF in place of the individual AE terms (fever, sore throat, rhinitis).

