2. STATISTICAL METHODS

2.1 GENERAL CONSIDERATIONS

The initial clinical study report will analyze only the main portion of the study, the 26-week open-label period. The 52-week OLE portion will be analyzed and reported separately, as will the extension to the OLE portion. Separate tables and data listings will be prepared for each portion of the study. Except where noted, the tables and listings will include only events occurring within the respective periods; however demographic, background and baseline events will be included for all the periods.

In general, continuous variables will be summarized by number of subjects, mean, standard deviation (SD), median, minimum, and maximum values. Categorical variables will be summarized by counts and percentage of subjects in each category.

Summary tables will present data within cohort, alphabetically, and overall if appropriate. Source data for the summary tables and statistical analyses will be presented as subject data listings, which include data collected on the electronic case report forms (eCRFs) as well as any derived efficacy variables for all enrolled subjects.

After the informed consent is signed, baseline seizure activity will be determined by the recordings in the subject's daily seizure calendars for a period up to 12 weeks prior to the first day of treatment. Post-baseline seizure activity will be determined by the days following the first day after the first treatment. (Since times of seizures were not recorded, determinations of whether seizures on the first day of treatment preceded or followed the treatment cannot be made.)

Baselines for the VAS and safety assessments are defined as the last non-missing value of the assessment before the first dose of treatment.

The study day for all assessments that are performed on or after the first day of treatment will be calculated as:

Study Day = date of the assessment – date of first treatment + 1.

For assessments performed before the first day of treatment, the study day calculation is:

Study day = date of the assessment – date of first treatment.

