5. PRIOR AND CONCOMITANT MEDICATIONS

Prior medications are defined as medications that started and stopped prior to the first dose of study drug. Concomitant medications are defined as medications (other than the study drug) taken on or after the first dose of the study drug during the study, regardless of when they were first taken. The summary of concomitant medications for the main 26-week open-label treatment period of the study will not include concomitant medications that start after the main 26-week open-label treatment period of the study; i.e. they will not include any concomitant medications starting on or after the first dosing day of the OLE period.

All investigator terms for medications recorded on the CRF will be coded using the World Health Organization (WHO) Anatomical Therapeutic Chemical (ATC) drug dictionary (Version WHO Drug Dictionary, March 2014). The number (percentage) of subjects who took prior and concomitant medications will be summarized by cohort and overall in the safety population, by ATC Classification and WHO Drug Preferred Term. Prior and concomitant Non AEDs and AEDs will be summarized separately.

A subject data listing of prior and concomitant medications will be provided, separately for non-AED and AEDs.

To define prior or concomitant medication, the following table describes how missing date information will be handled:

Partial Missing Start or Stop Date	Imputed Start Date	Imputed Stop Date
Missing year, month, and day	First dose date	
Missing month and day, and the year is present	First dose date if the year is the same as the year of first dose date, else first dose date of the OLE if the year is the same as the year of the first OLE dose date, else January 1 of the medication start year.	December 31 of that year
Missing day, but year and month are present	First dose date if the year and month are the same as the year and month of first dose date, else first dose date of the OLE if the year and month are the same as the year and month of the first OLE dose date, else the 1 st of the medication start month.	Last day of that month
Missing month, but year and day are present	Assume day is also missing and impute as above	Missing month imputed as December

If an imputed start date is later than the stop date, then the stop date (after any needed imputations) will be used instead for the imputed start date.

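### For children who enter the OLE, the partial-date rule can move main-period adverse events and medications out of the 26-week tables, even when a main-period visit had already recorded them

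*SAP*

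**What the plan says.** The imputation table in SAP 7.1 works through its branches in order.

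- **Year only.** "First dose date if the year is the same as the year of first dose date"; failing that, "else first dose date of the OLE if the year is the same as the year of the first OLE dose date"; failing that, 1 January of the start year.
- **Day missing.** The same order with month and year, so the second branch is "else first dose date of the OLE if the year and month are the same as the year and month of the first OLE" dose; the last resort is the first of the month.
- **Nothing known.** The first dose date.
- **Stop-date override.** A start imputed later than the stop date is replaced by the stop date. A stop date without a day becomes the end of its month; one without a month becomes 31 December.

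SAP 5 has the same table for medications. The result feeds the period split. Of the main-period adverse event analyses SAP 7.1 says "they will not include any AEs starting on or after the first dosing day of the OLE period", and of the medication summary SAP 5 says "they will not include any concomitant medications starting on or after the first dosing day of the OLE period".

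On reporting, SAP 2.1 says "The initial clinical study report will analyze only the main portion of the study, the 26-week open-label period", with the OLE reported separately. SAP 9 summarises adverse events for the OLE alone and for the whole study.

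Protocol 10.5.2 says "At each visit all adverse events that are observed, elicited by the Investigator, or reported by the subject, will be recorded". Neither imputation table uses the visit at which an item was recorded.

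**The concern.** Imputing an uncertain start to the first dose date is cautious, because it makes the event treatment-emergent. The OLE branch has no such effect. It is reached only when the date does not match the first-dose month or year. Without it, a date in the OLE-start month or year would fall back to the first of that month or to 1 January. That fallback is after the first dose and on or before the first OLE dose. The event is treatment-emergent either way, and a medication is concomitant either way, so the branch changes only the period.

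For medications it does even less for the OLE. SAP 9 counts any medication taken during the OLE, so one that continues is in the OLE table whatever its start date. The branch merely takes it out of the 26-week table. An antiepileptic drug added late in the main period could disappear there, although it bears on how the seizure change is read.

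SAP 7.1 also says that the main-period analyses cover events starting in that period. An event already recorded at Visit 6 or 7 plainly did. Cohorts were planned at up to 10 children (SAP 1.3.3), so one displaced event could change a cohort's incidence by 1/10 = 10 percentage points, if that child had no other main-period event with the same term.

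**Working it through.** The documents give no figure on this point, so there is none to reproduce. The check applies the rule to dates.

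**1. A worked case.** First dose 28 Oct 2015; Visit 6 at +119 days = 24 Feb 2016; Visit 7 at +182 days = 27 Apr 2016; first OLE dose at +183 days = 28 Apr 2016.

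- Ongoing event recorded at Visit 6, start known only as 2016. The year is not 2015 but matches the OLE year, so the imputed start is 28 Apr 2016, which is 183 − 119 = 64 days after it was recorded.
- Ongoing event recorded at Visit 7, start known only as April 2016. The imputed start is 28 Apr 2016, one day after it was recorded.

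Both leave the main-period tables and count as new in the OLE.

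**2. Assumptions for size.** The child enters the OLE; onsets are spread evenly over the main period; first doses are spread evenly over the 366 days of 2016; the first OLE dose is 183 days after the first dose, varied from 176 to 190 for the ±7-day window of Visit 7. The number of partial dates is unknown.

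**3. Day missing, item ongoing.** Every main-period onset in the OLE-start month moves. The days at risk are those of that month before the first OLE dose, that is, day of month minus 1. Over one year these sum to 7 × 465 (31-day months) + 4 × 435 (30-day months) + 378 (February) = 5,373. The 366 start dates give 366 OLE dates, one more than a full year, which adds 1: 5,374/366 = 14.7 days, and 14.7/183 = **8.0%** (7.7% to 8.4% over the range). A stop date known only to the same month gives the same result, because it is set to the month's end and the override does not act.

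**4. Year only, item ongoing.** Onsets move only if the first OLE dose falls in a later calendar year than the first dose. Numbering first-dose days k = 0 to 365, the main-period days in the later year are k − 183, which is positive for k = 184 to 365. That is 182 of 366 start dates (49.7%). The sum is 1 + … + 182 = 16,653; 16,653/366 = 45.5 days, and 45.5/183 = **24.9%** (23.9% to 25.8%). For the other half of start dates nothing moves.

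**5. Full stop date known.** The override keeps items that stopped before the first OLE dose. Share of main-period days moved:

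| Stop date after onset | Day missing | Year only |
|---|---|---|
| 3 days | 1.5% | 0.8% |
| 7 days | 3.3% | 1.9% |
| 30 days | 8.0% | 7.5% |

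**6. The reverse error.** A year-only OLE event in the calendar year of first dose is imputed to the first dose date and enters the main period. The days at risk are 183 − k for k = 0 to 182, which sum to 16,836; 16,836/366 = 46.0 days, or 46.0/364 = 12.6% of a 52-week OLE for ongoing items. Fully missing dates also go to the first dose date. For dates missing only the day, no OLE days move back.

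Year-only errors are therefore nearly balanced in days (45.5 out, 46.0 in), while day-missing errors run only out of the main period.

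**The case against.** **Reach is limited.** Only OLE entrants are affected. They must have completed all scheduled visits with at least 35% improvement (Protocol 9.3.2). A child whose adverse event ended participation in the main period has no OLE dose date, so that event cannot move. Serious events must be reported within 24 hours (Protocol 10.5.3.1), and start and end dates are minimum information for every event (Protocol 10.5.2), so partial dates should be exceptions. All of this stands and keeps the point small.

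**Nothing is lost from the programme.** Moved adverse events are counted in the OLE and entire-study tables, and listings show the actual dates. This stands too. But SAP 2.1 reports the OLE separately and prepares listings by period, so a reader of the initial report may see neither.

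**Sending an ambiguous date to the OLE is cautious for the OLE table.** That is a fair preference when the period is truly unknown. It does not justify an onset later than the visit that recorded the event.

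**SAP 7.1 gives treatment emergence as the purpose of the imputation.** Read literally, imputed dates might not be meant for the period split. But the OLE branch can affect nothing else, so period assignment is the natural reading.

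**The visit of first recording may not be in the database.** The protocol does not list it among the data required for each event or medication. The fix needs a fallback for that.

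**Conclusion.** The point holds in a bounded form. For children who enter the OLE, a true main-period adverse event or medication leaves the 26-week tables when its partial date matches the OLE-start month and not the first-dose month, or when a year-only date matches an OLE-start year that differs from the first-dose year. The exception is an item whose stop date is known to precede the first OLE dose. Some of these items receive an onset after the visit at which they were recorded.

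Under the assumptions above, about 8% of main-period days are exposed for ongoing items with the day missing, and about 25% for ongoing year-only items. Both apply only to an unknown, probably small, number of partial dates.

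A reader might infer more, and the documents do not support it:

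- **That every date matching the OLE-start month or year moves.** The first-dose branch is tested first, so a year-only date stays in the main period when both doses fall in one calendar year. Only about 33% of main-period onsets in the OLE-start year move, even for ongoing items.
- **That the table can only take events away from the 26-week report.** That is true of the OLE branch but not of the whole table, which also brings year-only and fully undated OLE events into the main period.
- **That events vanish.** Adverse events remain in the OLE and entire-study tables.

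**What to change.** In the tables in SAP 7.1 and SAP 5:

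1. State that imputed dates are used to assign items to the main period or the OLE, and that an imputed start may not be later than the visit at which the item was first recorded. Keep the stop-date override.
2. If that visit is on or before the first OLE dose date, impute to the later of the first dose date and the earliest date that the partial date allows. Dates that lie wholly before the first dose keep the present fallback, and the cap in step 1 takes precedence for items recorded before the first dose.
3. Use the first OLE dose date only for items first recorded after the OLE began whose partial date is compatible with an OLE start. This includes year-only dates in the first-dose year, and fully missing dates should be handled in the same way. That deals with the reverse error.
4. If the visit of first recording is not in the database, take it from the visit records. Otherwise list and count the affected items in the 26-week report.

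The cost is a few lines of SAP wording, a small programming change and, where step 4 applies, some retrieval of visit records. Main-period counts may rise slightly.

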7.1.1 Deaths, Serious and Other Significant Adverse Events

The listings of deaths, SAEs, and AEs leading to study drug discontinuation will be provided.

7.2 CLINICAL LABORATORY PARAMETERS

Laboratory assessments include hematology, clinical chemistry, and urinalysis:

- Clinical Chemistry: Total Bilirubin, Aspartate Aminotransferase (AST), Alanine Aminotransferase (ALT), Blood Urea Nitrogen (BUN), Glucose, Potassium, Sodium, Calcium, Alkaline Phosphatase, Chloride, Creatinine, Carbon Dioxide (CO₂).
- Hematology: Hemoglobin, Hematocrit, Erythrocytes, Leukocytes + differential, Thrombocytes (platelet count).
- Urinalysis: pH, Color, Transparency, Specific Gravity, Urobilinogen, Ketones, Protein, Glucose

All laboratory parameters will be presented in SI units. Quantitative results (including actual value and change from baseline) will be summarized using descriptive statistics by baseline and

post-baseline visit for each laboratory test group above. Laboratory test results were evaluated as normal, abnormal (not clinically significant) or abnormal (clinically significant). The number and percentage of subjects of each category will be summarized by baseline and post-baseline time point for each parameter.

All laboratory data will be included in the listings. A pregnancy listing will be provided separately.

7.3 VITAL SIGNS, NEUROLOGICAL AND PHYSICAL EXAMINATIONS FINDINGS, ECG, EEG, AND CSSRS

7.3.1 Vital Signs

Vital signs include weight, height, temperature, blood pressure (BP), and pulse rate.

All vital signs will be presented in SI units. Quantitative results (including actual value and change from baseline to each post-baseline visit) will be summarized using descriptive statistics by baseline and post-baseline time point for each parameter.

Vital sign test results will be assigned an LNH classification according to whether the value was below (L), within (N), or above (H) the normal reference range. The number and percentage of subjects in each category will be summarized by baseline and post-baseline time point for each parameter. The normal reference ranges are: Systolic Blood Pressure: 110-130 (mmHg); Diastolic Blood Pressure: 70-90 (mmHg); Temperature: 97.0–101.5(F) or 36.1 – 38.61(C); Pulse Rate: 60-100 beats/min. For weight, the number (%) of subjects with $\geq 7\%$ change from baseline will be summarized by post-baseline time point.

A listing of vital signs, including abnormal flags, will be provided.

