Protocadherin (PCDH)19- female-pediatric epilepsy (FPE), also known as PCDH19 female-limited epilepsy (FLE) or epilepsy in females with mental retardation (EFMR), is a serious epileptic syndrome characterized by early-onset cluster seizures, cognitive and sensory impairment of varying degrees, and behavioral disturbances in some individuals.¹ This disorder is associated with a mutation of the PCDH19 gene, the gene that encodes for protocadherin19 on the X chromosome.^{2,3} The mechanism by which this mutation contributes to the development of epilepsy and intellectual impairment is not fully understood, however protocadherin19 is a transmembrane protein of calcium-dependent cell-cell adhesion molecules that is strongly expressed in neural tissue (e.g., hippocampus, cerebral cortex, thalamus, amygdale), and which appears to be related to synaptic transmission and formation of synaptic connections during brain development.³ Research suggests impairment of GABAergic signaling both at the agonist and receptor levels is present in girls with PCDH19 mutations and pediatric-onset epilepsy.⁴

The hallmark characteristics of PCDH19-FPE are clusters of seizures which start in infancy or early childhood often associated with fever or immunization.⁵⁻⁷ Patients with PCDH19-FPE may experience individual seizures in addition to clusters and multiple seizure types. In some patients, seizures improve as patients reach puberty, possibly due to increased endogenous levels of progesterone and allopregnanolone.⁸⁻¹⁰

Background on CDKL5 Disorder

CDKL5 disorder or CDKL5 stands for cyclin dependent kinase like 5, and is located on the X chromosome. The CDKL5 gene was previously called STK9. CDKL5 is a rare X linked genetic disorder that results in early onset, difficult to control seizures, and severe neuro-developmental impairment. ¹⁹

Most of the children affected by CDKL5 present with irritability in the perinatal period, early epilepsy, hand stereotypies, severely impaired psychomotor development and severe hypotonia. In contrast to classical Rett syndrome they also may have absence of a classic regression period, poor eye contact, generally normal head circumference and other growth parameters and relative absence of autonomic dysfunction. ¹⁹

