Seizures occur without a fever. However, these children are very sensitive to infections and frequently have seizures when they are ill or have a fever. Seizures can also be triggered by slight changes in body temperature that are not caused by infection for example a warm or hot bath water or hot weather. Many children have photosensitive seizures. Emotional stress or excitement can also trigger seizures in some children. ^{17,18}

Children usually develop normally in the early years. After age 2, they may lose developmental milestones or do not progress as quickly as they get older and have more seizures. There seems to be a correlation between frequency of seizures, how often status epilepticus occurs, and the degree of developmental delay in children. Around 6 years of age, cognitive problems in some children may stabilize or may start improving. However, most children with Dravet syndrome have some degree of developmental disability that persists. ^{17,18}

Other problems that may be seen include: low motor tone – can lead to painful foot problems, unsteady walking, some may develop a crouched gait, chronic infections, low humoral immunity, growth and nutrition problems, problems with the autonomic nervous system and behavioral or developmental problems such as autism spectrum disorder. ^{17,18}

BACKGROUND ON LGS AND CSWS

Lennox-Gastaut syndrome is a severe form of epilepsy. Seizures usually begin before 4 years of age. Seizure types, which vary among patients, include tonic, atonic, atypical absence, and myoclonic. There may be periods of frequent seizures mixed with brief, relatively seizure-free periods. Most children with LGS experience some degree of impaired intellectual functioning or information processing, along with developmental delays, and behavioral disturbances. Lennox-Gastaut syndrome can be caused by brain malformations, perinatal asphyxia, severe head injury, central nervous system infection and inherited degenerative or metabolic conditions. In 30-35 percent of cases, no cause can be

found. Many cases of LGS have had genetic mutations associated with the diagnosis clinically. These can include known encephalopathic epilepsy genes in Rett Syndrome, CNTNAP1, XP22.33, SCN2A, GABR3, Shank2, Shank3, and other genetic conditions associated with LGS-type clinical epilepsy. Non –degenerative genetic types of LGS or idiopathic refractive cases may respond to the neurosteroid mechanism of ganaxolone.

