9.3.2 Inclusion Criteria

- 1. Have parent or legal guardian available and willing to give written informed consent, after being properly informed of the nature and risks of the study and prior to engaging in any study-related procedures.
- 2. Outpatients between 2 and 18 years of age at time of consent.

3. In the opinion of the investigator have confirmed PCDH19 genetic mutation, confirmed CDKL5 genetic mutation or Dravet Syndrome confirmed by a SCN1A mutation, or genetic epilepsy testing confirming a LGS or CSWS condition associated with this genetic phenotype. Refractive cases of LGS or CSWS that remain idiopathic or have prior history of steroid or ACTH response can also be entered if documentation confirms specific genetic defects are not found and prior steroid response clinically occurred.

4. Seizure criteria:

- a. Have uncontrolled cluster seizures (3 or more seizures over the course of 12 hours) every 6 weeks or less during baseline, or bouts of status epilepticus on intermittent basis, or
- b. Have uncontrolled non-clustered seizures (focal dyscognitive, focal convulsive, atypical absences, hemiclonic seizures, spasms, or tonic-spasm seizures) with a frequency ≥4 seizures per 28-day period during baseline, or
- c. Have ≥4 generalized convulsive (tonic-clonic, tonic, clonic, atonic seizures) per 28-day baseline period during baseline, or
- d. Have subclinical CSWS syndrome with or without clinical events on EEG
- 5. Subjects should be on a stable regimen of AED medication, and generally in good health.
- 6. Parent or guardian is able and willing to maintain an accurate and complete daily written seizure calendar for the duration of the study.
- 7. Able and willing to take study medication with food, two or three times daily. Ganaxolone must be administered with food.

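### SAP 7.3.1 classes vital signs at every age from 2 to 18 against one fixed set of limits, so the low/normal/high table and listing flags discriminate poorly in younger children

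*SAP*

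**What the plan says.** The classification rule in SAP 7.3.1 is: "Vital sign test results will be assigned an LNH classification according to whether the value was below (L), within (N), or above (H"). The yardstick is a set of reference limits listed in the same paragraph: "Systolic Blood Pressure: 110-130 (mmHg); Diastolic Blood Pressure: 70-90 (mmHg"), temperature 97.0 to 101.5 F (36.1 to 38.61 C), and "Pulse Rate: 60-100 beats/min". There is one set for everyone, with no adjustment for age, sex or height and no source.

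The output is a count table: "The number and percentage of subjects in each category will be summarized by baseline and post-baseline time point for each parameter". The section also promises a listing with abnormality flags. It defines no other flag, so I take these to be the low and high classes.

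The categories are not the only analysis. The same section states: "Quantitative results (including actual value and change from baseline to each post-baseline visit) will be summarized using descriptive statistics", for each parameter.

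The population is set by Protocol 9.3.2: "Outpatients between 2 and 18 years of age at time of consent". The suggested titration tables in Protocol Appendix 4 start at 15 kg, so small children are expected. On fever, the PCDH19 background in Protocol section 7 describes "clusters of seizures which start in infancy or early childhood often associated with fever or immunization". The supplied protocol is version 6.0 (April 2016). The SAP refers to Amendment 8.1, which was not supplied, so the age range is taken from version 6.0.

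**The concern.** A reference-range table is useful only if most untreated children fall in the normal class, so that movement out of it means something. Blood pressure and pulse depend on age across 2 to 18 years. A single systolic floor of 110 and diastolic floor of 70 may therefore put many younger children in the low class before the first dose. They then stay there at every visit, and a further fall does not change the table.

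This matters because safety and tolerability are the secondary objective and vital signs are a named safety endpoint (SAP 1.1.2 and 1.2.3). Protocol 9.4.5 has families warned about rapid changes of posture, so downward movement in pressure is a direction in which the flag should discriminate. Laboratory and ECG results also receive a clinical-significance category (SAP 7.2 and 7.3.3), but vital signs do not. For them the low/normal/high class is the only abnormality flag the SAP defines. With up to 10 subjects planned per cohort (SAP 1.3.3), readers will lean on individual flags.

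For temperature, the ceiling means a reading as high as 101.5 F is filed as normal in a trial that includes the PCDH19 cohort.

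**Working it through.** **1. The plan's own figure.** The temperature limits are given in two units. With C = (F - 32) x 5/9:
- (97.0 - 32) x 5/9 = 36.11
- (101.5 - 32) x 5/9 = 38.61

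Both match the SAP, so 101.5 F is the intended ceiling and not a slip in one unit.

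**2. A result that does not depend on the spread.** If a measurement in an age group is roughly normal with mean m and standard deviation s, the share flagged low is Phi((limit - m)/s). This exceeds one half exactly when m is below the limit, whatever s is. So more than half are low whenever mean systolic pressure is below 110, or mean diastolic pressure is below 70.

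**3. Size under assumptions.** The documents give no paediatric norms and no age distribution. The means and SDs below are assumptions, shown as ranges.
- Systolic below 110, mean 95, SD 8: Phi(15/8) = Phi(1.875) = 97.0%. Mean 105, SD 10: Phi(5/10) = Phi(0.5) = 69.1%. Means of 95-105 with SD 8-10 therefore give 69-97%.
- Systolic, mean 110: 50%. Mean 115, as might apply to adolescents: Phi(-5/8) = 26.6% at SD 8 and Phi(-5/12) = 33.8% at SD 12, so 27-34%.
- Diastolic below 70, mean 55-65, SD 8-10: from Phi(5/10) = 69.1% to Phi(15/8) = 97.0%, so again 69-97%.
- Pulse above 100: mean 90, SD 10 gives 1 - Phi(1) = 15.9%. Mean 110, SD 10 gives 1 - Phi(-1) = 84.1%. A range of 16-84% over means of 90-110 (SD 10-15) shows strong dependence on the assumed mean, not saturation.

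**4. What the count table can register.** Take SD 10 and a fall of 10 mmHg in the group mean. Expected numbers low, per 10 children:
- Mean 115 to 105: 30.9% to 69.1%, or 3.1 to 6.9.
- Mean 105 to 95: 69.1% to 93.3%, or 6.9 to 9.3.
- Mean 95 to 85: 93.3% to 99.4%, or 9.3 to 9.9.

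The same fall moves 3.8 children in the first case (6.9 - 3.1) and 0.6 in the last (9.9 - 9.3). For one child, a fall from 105 to 95 is low at both visits and no category changes. The -10 mmHg does enter the change-from-baseline summary.

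**5. Temperature.** The documents give no fever threshold. If it were 100.0, 100.4 or 101.0 F (assumed), the top 1.5, 1.1 or 0.5 F of the normal band would be fever classed as normal (101.5 minus each threshold).

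**The case against.** The strongest reply is that this is a supplementary descriptive display in an uncontrolled proof-of-concept study. No test, sample size, endpoint or stopping rule in the supplied documents uses these classes. Actual values and changes from baseline are summarised, every value is listed, and a clinically significant worsening is an adverse event under Protocol 10.5.1. Protocol 9.7.6 also plans to flag critically significant vital-sign changes in listings. The magnitudes rest wholly on assumed norms, and older children would be flagged far less often. All of this stands. It limits the finding to the table and the flags but does not make the ranges suitable for them.

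A reader might infer three stronger things that the documents do not support.
- That a real fall in blood pressure would be invisible. It would not, because the quantitative summaries in the same section do not use the limits.
- That the protocol says slight temperature changes provoke seizures in the children analysed. The sentence "Seizures can also be triggered by slight changes in body temperature that are not caused by infection" is in the Dravet background, and SAP 1.3.1 reports that no Dravet subjects were recruited. The PCDH19 text quoted above is the relevant one, and it speaks of fever.
- That the temperature ceiling lets fever confound the seizure counts. Those counts come from daily calendars, temperature is taken only at visits, and no seizure analysis uses the temperature class. Readings above 101.5 F are still classed high.

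**Conclusion.** The point holds in limited form and should be corrected. One unbanded set of limits applied to ages 2 to 18 makes the low/normal/high table and the abnormality flags poor discriminators for blood pressure in younger children.

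The qualitative result, more than half flagged low, needs only a roughly symmetric distribution and a group mean below 110 systolic or 70 diastolic. The 69-97% figure rests on assumed means and SDs, and it does not carry over to adolescents. The case on pulse is weaker, because the share flagged depends heavily on the assumed mean. On temperature, the firm statement is that readings up to 101.5 F are classed normal. How many fevers this covers depends on a threshold that the documents do not give.

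The consequence is confined to one descriptive safety table and the listing flags.

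**What to change.** In SAP 7.3.1:
- Replace the single blood pressure and pulse ranges with pre-specified paediatric reference ranges from a cited source, banded by age, and by age and sex for blood pressure. State whether age at baseline or at the visit selects the band, since a child may cross bands over 26 + 52 = 78 weeks.
- Add shift tables from each child's baseline category to each later visit. The section already uses a within-child criterion for weight (a change of at least 7%), so this follows its own practice.
- Lower the temperature ceiling used for flagging to a pre-specified, sourced fever threshold.
- Keep the summaries of actual values and changes as they are.

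The cost is a lookup table and one added table shell. Age, gender and height (SAP 4.1) and the vital signs are already collected, so no new data are needed.
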